Our long-term goal is to develop a biomarker of treatment in patients receiving ECT. By having this biomarker, practitioners could move towards individualized treatment parameters. We hypothesize that ictal power and post-ictal infra-slow waves will be associated with clinical response and the choice of anesthetic agent will accentuate ictal or post-ictal morphology. We propose a pilot project using dcEEG to look at infra-slow waves in depressed patients receiving ECT randomized to ketamine or methohexitol. The rationale for this project is to identify biomarkers of treatment adequacy in ECT, which could lead to decreased morbidity and mortality with the procedure and lessen the burden of depression in our patient population.

Aim 1: Identify EEG biomarkers related to clinical response

PROTOCOL TITLE:

Hypothesis 1.1: Ketamine will be associated with increased ictal power and increased post-ictal suppression compared to methohexital

Hypothesis 1.2: Methohexital will be associated with post-ictal infra-slow waves

Hypothesis 1.3: Increased ictal power and infra-slow waves will be associated with clinical outcomes

At the completion of this pilot project, we expect to identify infra-slow characteristics using dcEEG that correspond with clinically effective treatment. We plan to further evaluate these phenomena as a potential biomarker of treatment adequacy with the goal of individualizing ECT treatments and improving standard of care.

2. Background

[figure not shown]
Historically it was thought that inducing a seizure was all that was needed to produce the clinical effects seen in ECT, but multiple studies across the past 8 decades have shown varying rates of efficacy and severity of side effects based on ECT stimulus parameters. We learned empirically that electrode placement (bitemporal versus unilateral) and stimulus parameters that affect electrical pulse and pulse train matter [10]. However, practitioners continue to focus on total charge as the primary metric, largely ignoring the role individual stimulus parameters play in the equation.

A biomarker of treatment response would help in evaluating clinical efficacy and accelerate evaluation of individual ECT parameters. There have been many potential biomarker for depression including hormones, cytokines, and neuro-imaging. These investigations have

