Exclusion Criteria: 1) Defined neurological or neurodegenerative disorder (e.g., history of head injury with loss of consciousness > 5 minutes, epilepsy, Alzheimer's disease); 2) other psychiatric conditions (e.g., schizophrenia, schizoaffective disorder, bipolar disorder); and 3) current drug or alcohol use disorder, except for nicotine and marijuana 4) adults unable to consent, pregnant women, prisoner; 5) Have contraindications to methohexitol and ketamine as described in the package inserts; 6) non-English speakers; 7) Patients that cannot tolerate Methohexitol and Ketamine.

5. Number of Subjects

26 subjects meeting the inclusion criteria will be recruited for this investigation. Our total sample size ($n = 26$) allows for a conservative 15% attrition rate leaving a final sample size of 22. This recruitment rate of 26 subjects per year will complete subject recruitment 1 year after study initiation. Sample size calculation is based on the 2004 Perera et al. paper examining ictal power between a threshold group and suprathreshold group (Cohen's $d = 1.19$) with variances of .24 and .25 respectively. Assuming a power of .8 and a two-sided alpha (.05), we will need 11 patients in each group to adequately power our analysis, which is in line with our recruitment projections.

6. Study Timelines

Individual subjects will have 4 points (T1-T4) in the study with the endpoint being their last treatment. ECT is done three times weekly and a typical series includes 8-12 treatments. This means that patients will be enrolled and participating in research for approximately one month. The study period will be one year long with an additional three months for analysis for a total of 15 months.

7. Study Endpoints

The primary endpoints include change in depression rating scale. Changes in depression rating will be compared with total ictal power and postictal suppression along with presence and power of infra-slow waves on dcEEG.

8. Research Setting

Patients will be recruited through the UNMH ECT consult service. All data collection will take place at the UNM Center for Psychiatric Research, or the ECT service at the University of New Mexico. All clinical assessments and neuropsychological testing will be conducted in an interview room or in a private patient room.

9. Resources Available

PROTOCOL TITLE:

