Investigators: The PI ([name]) is a board-certified Psychiatrist and Assistant Professor at UNM. He has been on the neuromodulation service and doing ECT for two years. He has a recent publication on electrode placement and ECT. He has .5 FTE devoted to completing this project as this constitutes his Master's Thesis in the MSCR program. He plans to apply to the CTSC for pilot grant funding.

10. Prior Approvals

Departmental Review Form signed by Department Chair uploaded into Click under "supporting documents."

11. Multi-Site Research

NA

12. Study Procedures

Clinical Assessments: The primary clinical response measure will be change in the QIDS C and QIDS SR [15]. The trained clinical rater will use the structured interview for the HDRS-24 to examine inter-rater reliability [16]. The initial visit will also include the Maudsley Staging Method Form for treatment resistance [17], ECT Appropriateness Scale to assess the indication for ECT [18], Medical History form to gauge overall medical burden, and Edinburgh Handedness Inventory [19].

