Study Protocol: Subjects will receive their baseline depression and cognitive assessment 0 to 48 hours prior to the first ECT session (T1). One day after the sixth ECT treatment (T3), subjects will receive their second depression and cognitive assessment. Treatments will continue thrice weekly until clinical response, which

PROTOCOL TITLE:

typically occurs between six and twelve treatments. The final assessment will occur after their last ECT treatment in the series (T4) and will include depression and cognitive assessments. DcEEG data will be collected at T1-T4 using a non-invasive cap that covers the patient's head. Per standard of care, change of electrode placement will be assessed at the midpoint (T2) by the treating psychiatrist. If the patient is not responding to ECT they may be switched from RUL to bitemporal placement. This assessment will not be affected by the research protocol.

13. Data Analysis

See effect size calculation in question #5 for hypothesis 1.1. To the best of our knowledge, spreading depression has never been studied in ECT (aside from our preliminary findings). We will use the effect size for hypothesis 1.1 to guide us. In terms of analyzing the mean power of the waves noted, we plan to calculate the sum of the mean power per epoch across T1-T4 data points to get total ictal power, as well as smaller epochs to calculate total infra-wave power and post-infra-wave suppression. We will also use chisq to compare number of infra-slow waves and t-tests to compare power of infra-slow waves and total ictal power of seizures and post-ictal suppression in the methohexitol group. We do not expect to see infra-slow waves in the ketamine group.

14. Provisions to Monitor the Data to Ensure the Safety of Subjects

Methohexitol and ketamine are both standard of care anesthetic agents used in ECT and the dcEEG device is worn on the scalp and is non-invasive. If the patient does not tolerate the anesthetic chosen, then they will be switched to the other anesthetic and act as a cross-over cohort. The medications and ECT device used in this study are standard of care. In the unlikely event that at the midpoint assessment (6 months) greater than 50% of patients have refused to wear the EEG cap, our study will not be sufficiently powered and will be terminated.

15. Withdrawal of Subjects

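### Section 13's tests do not match the hypotheses: t-tests worded for one arm only, a chi-square with no unit, no switching rule, and no analysis for Hypothesis 1.3

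*Combined protocol and SAP*

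**What the plan says.** Section 1 sets three hypotheses under Aim 1:

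- 1.1: "Ketamine will be associated with increased ictal power and increased post-ictal suppression compared to methohexital".
- 1.2: "Methohexital will be associated with post-ictal infra-slow waves".
- 1.3: "Increased ictal power and infra-slow waves will be associated with clinical outcomes".

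Section 5 sizes the trial on ictal power (d = 1.19, power .8, two-sided alpha .05) and concludes that "we will need 11 patients in each group to adequately power our analysis". Section 13 opens by referring Hypothesis 1.1 back to that calculation.

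Section 13 then defines total ictal power as a sum over T1 to T4. It assigns a chi-square to the count of infra-slow waves and adds "t-tests to compare power of infra-slow waves and total ictal power of seizures and post-ictal suppression in the methohexitol group". It expects no infra-slow waves under ketamine.

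On the link to outcome, Section 7 says: "Changes in depression rating will be compared with total ictal power and postictal suppression along with presence and power of infra-slow waves on dcEEG". Section 12 says "The primary clinical response measure will be change in the QIDS C and QIDS SR", and on recordings, "DcEEG data will be collected at T1-T4 using a non-invasive cap". Section 14 has patients who do not tolerate their agent change to the other one and treats them as a crossover group.

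**The concern.** Section 13 is the only place where tests are named, so an analyst would follow it. It falls short in four places.

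- The t-test sentence confines ictal power and post-ictal suppression to one arm, so it does not carry out the comparison the trial was sized for.
- The chi-square does not say whether it counts waves, recordings or patients. Recordings from one patient are not independent.
- Switched patients have no stated place in either comparison.
- The association with clinical outcome, which Aim 1 is about, has no named estimate or test. The pairing of scale and EEG measure to report could therefore be settled after the data are seen.

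**Working it through.** **1. The plan's own figure.** Inputs from Section 5: d = 1.19, two-sided .05, power .8. Normal approximation: n = 2 × ((1.960 + 0.842)/1.19)² = 11.09 per group. At 11 per group, power is 0.797 (normal) or 0.756 (noncentral t). The stated 11 is reproduced closely, as a two-group comparison of ictal power. For attrition, 26 × 0.85 = 22.1. The sizing therefore presupposes a between-arm test.

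**2. Section 13 against that.** A t-test needs two sets of values, and the sentence names only methohexital. For infra-slow-wave power the restriction may be deliberate: no ketamine waves are expected, and no rule scores an absent wave as zero. For ictal power and post-ictal suppression it contradicts Hypothesis 1.1.

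**3. Chi-square if recordings are pooled (one open reading).** Assumptions: 11 patients × 4 recordings = 44 per arm, yes/no per recording, equal wave rates in both arms, ICC 0.1 to 0.7. The documents give no ICC or rate. With design effect 1 + 3 × ICC, the approximate error is 2 × (1 − Φ(1.96/√DE)): 8.6%, 15.5% and 21.5% at ICC 0.1, 0.3 and 0.5. Beta-binomial simulation gives the following ranges over ICC 0.1 to 0.7:

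| Wave rate | Uncorrected | Continuity-corrected |
|---|---|---|
| 2% | 2.5% to 17% | 0.2% to 2.8% |
| 5% | 7.9% to 28.5% | 1.4% to 10.1% |
| 10% | 9.7% to 31.9% | 3.3% to 17.8% |
| 50% | 8.0% to 27.0% | 5.1% to 21.8% |

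**4. Chi-square with one value per patient.** By enumeration at 11 v 11, the maximum error is 5.3% uncorrected and 1.7% for Fisher, so defining the unit removes the inflation. The cells stay sparse. For 4/11 v 0/11 the smallest expected count is 4 × 11/22 = 2, and:

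- uncorrected: 22 × 44²/(11 × 11 × 4 × 18) = 4.89, p = 0.027;
- corrected: 22 × 33²/(11 × 11 × 4 × 18) = 2.75, p = 0.097;
- Fisher: 2 × C(11,4)/C(22,4) = 2 × 330/7315 = 0.090;
- Boschloo: 0.033.

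Against 0/11, Fisher needs 5/11: 2 × 462/26334 = 0.035. If the true methohexital rate is 50% and ketamine stays at zero, power is P(X ≥ 5) = 73% for Fisher and P(X ≥ 4) = 89% for Boschloo.

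**5. Switching.** Suppose one patient randomised to ketamine changes agent and then shows a wave. By randomised arm, 5/11 v 0/11 (Fisher p = 0.035) becomes 5/11 v 1/11: 2 × (462 × 11 + 462)/74613 = 0.149. For summed ictal power, assuming a change after T1 and an equal effect at each time point, one switched patient in one arm shrinks the difference by 3/4 × 1/11 = 6.8%, and two by 13.6%.

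**6. Hypothesis 1.3.** It names ictal power and infra-slow waves. Section 7 splits the waves into presence and power, so there are two or three EEG measures. With the two QIDS scales of Section 12 this gives 4 to 6 pairs. With no true association, the chance of at least one p < .05 is 1 − 0.95⁴ = 19% to 1 − 0.95⁶ = 26% if the pairs are independent. By simulation at n = 22 it is about 12% to 23%, assuming correlations of 0.6 to 0.9 between scales and 0.3 to 0.6 among EEG measures.

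Arm matters here. If a proportion p of methohexital patients and no ketamine patients show waves, wave presence correlates with arm at √(p/(2 − p)), which is 0.58 to 0.73 for p = 0.5 to 0.7. In a model with arm and wave presence only, the wave coefficient is then the within-methohexital difference.

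Detectable correlation at 80% power, tanh(2.802/√(n − 3)): 0.57 at n = 22 and 0.76 at n = 11.

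**The case against.** The strongest reply is that the t-test wording is loose drafting. A t-test within one group has no comparator and cannot be run literally, Section 13 points to a two-group calculation, and Hypothesis 1.1 names both agents. This stands. A reader might infer that no between-arm test was planned or that the sample size is wrong; the documents support neither.

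A reader might also infer that the chi-square will be anticonservative. The documents do not say recordings are pooled, and Section 7 speaks of the presence of waves, which allows a per-patient reading. The ICCs and rates are assumed. Since no ketamine waves are expected, a common rate under the null could be very low, where the corrected test is below 5%. What stands is that the unit is not stated.

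A third tempting reading is eight pairs for Hypothesis 1.3, with 1 − 0.95⁸ = 34%. That counts post-ictal suppression, which Section 7 lists but Hypothesis 1.3 does not name. Nor do the documents say that a pair will be picked after the data are seen; they only leave it possible.

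Finally, this is a pilot with further evaluation intended, and Fisher's test is not the only valid choice. Both are fair. Neither removes the need to state the contrast, the unit and the leading association.

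**Conclusion.** The concern holds as a defect of specification that should be fixed; it is not a fatal flaw. Two parts go beyond missing detail: the t-test sentence, followed as written, omits the contrast that Section 5 sizes, and the chi-square sets no independent unit. The pooled error of about 8% to 32% is conditional on pooling, an uncorrected test, and assumed rates of 5% to 50% and ICCs of 0.1 to 0.7. The dependence on the version of the test at 4/11 v 0/11 needs no such assumptions, and a zero ketamine cell is what the plan itself expects. The absence of a rule for switched patients affects both comparisons. For Hypothesis 1.3 the gap is mostly missing detail; the concrete part is that arm must be accounted for, because waves are expected under one agent only. Low precision for Hypothesis 1.3 reflects the size of the pilot and is not caused by the omission.

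**What to change.** Amend Section 13 as follows.

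1. **Hypothesis 1.1.** Specify two-sided .05 between-arm t-tests (ketamine v methohexital, by randomised arm) of per-patient total ictal power and post-ictal suppression. Describe wave power only among patients with waves.
2. **Hypothesis 1.2.** Use one value per patient (any infra-slow wave across T1 to T4, yes/no), and name in advance a per-patient test suited to sparse cells. The sponsor chooses: Boschloo rejects from 4/11 v 0/11, while Fisher needs 5/11 and lowers power from 89% to 73% at a true rate of 50%.
3. **Switched patients.** For both comparisons, make the analysis by randomised arm primary. Add a sensitivity analysis by agent received at each recording, or one excluding switched patients. Reconcile this with the crossover group in Section 14.
4. **Hypothesis 1.3.** Estimate, per patient and with 95% CI, the association of depression change with total ictal power and with wave presence, each adjusted for randomised arm. If no ketamine patient shows waves, the separate wave model already gives the within-methohexital difference, so no second analysis is needed. The sponsor names one leading scale and one leading EEG measure; the other pairs are exploratory.

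The cost is wording only, with no new data or patients. Intervals for Hypothesis 1.3 will be wide whichever analysis is named.

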The electroencephalogram (EEG) is used to monitor seizure activity during ECT. EEG measures have been evaluated as markers for treatment adequacy, but were found to be ineffective, mainly due to EEG's inability to discriminate between dosages in unilateral electrode placement and the weak association between EEG characteristics and clinical outcome [1]. Our neuromodulation group has recently deployed direct current EEG (dcEEG) in patients undergoing ECT. DcEEG differs from normal EEG by its ability to measure slow cortical potentials (SCPs) in low frequencies. SCPs are shifts in the cortical electrical activity lasting from several hundred milliseconds to several seconds. These SCPs may offer insight into inhibitory processes heretofore unexplored. We have captured large infra-slow brain activity using dcEEG on patients receiving ECT. This activity is consistent with a type of SCP called cortical spreading depression (SD). These so-called "brain tsunamis" are powerful, propagating waves of near-complete depolarization resulting in suppression of neuronal activity and are associated with the pathophysiology of stroke, traumatic brain injury, epilepsy, and migraines [2]. However, studies in rats and mice have associated SD in healthy brain tissue with neurogenesis [3, 4]. One in-vivo study with rats found that SD happened during ECT and suggested SD-induced neurogenesis as the neurobiological element underpinning ECT's clinical effectiveness [5]. We can observe the role SDs play in ECT based on the anesthesia used.

Ketamine is an induction agent often used in ECT. Ketamine reduces seizure threshold and was thought to produce superior results given the longer and more pronounced seizures seen in ECT. However, multiple randomized controlled trials (RCTs) have shown no difference in clinical efficacy between ketamine and other induction agents [6]. Unlike other induction agents, ketamine blocks SDs [7]. This may explain why ketamine has not delivered on its promise. While it accentuates seizure production and strength, it may block SD-induced neurogenesis.

Methohexitol is another induction agent used in ECT. Although methohexitol decreases seizure length and raises seizure threshold in comparison to ketamine, there is no difference in clinical outcome between methohexitol and ketamine when used with ECT [8, 9].

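### The t-test on infra-slow power has no usable ketamine arm on the plan's own expectation, because power is tied to waves that are seen and none are expected under ketamine

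*Combined protocol and SAP*

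**What the plan says.** Hypothesis 1.2 in Section 1 reads "Hypothesis 1.2: Methohexital will be associated with post-ictal infra-slow waves". The reason for expecting a contrast is in the same section: "Unlike other induction agents, ketamine blocks SDs".

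Section 13 sets out the analysis in one paragraph.

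- It opens the power analysis with "In terms of analyzing the mean power of the waves noted".
- It uses "smaller epochs to calculate total infra-wave power and post-infra-wave suppression", without giving the length or position of those epochs.
- For counts: "We will also use chisq to compare number of infra-slow waves".
- For power: "t-tests to compare power of infra-slow waves". The same sentence covers ictal power and ends "post-ictal suppression in the methohexitol group", naming no comparator.
- It closes with "We do not expect to see infra-slow waves in the ketamine group".

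No section defines a time window or frequency band in which infra-slow power is measured in every recording. No section says what value a recording without a wave receives. Section 7 names both presence and power of infra-slow waves among the measures to be set against change in depression rating. Section 5 sizes the trial on ictal power, and Section 13 borrows that effect size for infra-slow waves.

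**The concern.** A two-sample t-test needs a set of values with some spread in each arm. Here the measurement depends on detecting a wave, and the plan predicts no detections in one arm. Three outcomes are possible, and none is a sound randomised comparison of power.

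1. Power exists only where a wave is seen. The ketamine sample is empty and the test cannot be run.
2. A recording without a wave is scored zero. The ketamine arm is constant, and the test only asks whether the methohexital mean differs from zero. Any patient with a wave already answers that, so little is added to the presence comparison.
3. A few ketamine patients show waves. The test then compares patients selected by a post-randomisation event that the anaesthetic is meant to influence.

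Because the plan does not choose among these, the choice would fall to the analyst after the data are seen, and the options give different answers. If the last sentence of the t-test passage means a test within the methohexital group alone, there is again no ketamine comparison.

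**Working it through.** **Inputs from the plan.** Section 5: d = 1.19, variances .24 and .25, power .8, two-sided alpha .05, 11 per group, 26 recruited with 15% attrition. Section 13: no waves expected under ketamine. The documents give neither the wave rate under methohexital nor the distribution of wave power.

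**The plan's own figure.** n per group = 2(1.96 + 0.84)² / 1.19² = 15.68 / 1.416 = 11.1, so 12 by the normal approximation. The noncentral t gives 12.12, so 13. The stated 11 is within two patients of both. Attrition: 26 × 0.85 = 22.1, so 22. This calculation is not the problem. It does assume two arms of similar spread, which a constant ketamine arm cannot have, so the borrowed d does not carry over to infra-slow power scored with zeros.

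**Empty arm.** With 11 methohexital values and no ketamine values, the two-sample t-test returns no statistic.

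**Zero-scored arm.** Let s² be the methohexital variance.

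- Pooled variance = (10s² + 10 × 0)/20 = s²/2.
- Standard error = √(s²/2 × 2/11) = s/√11, which is the one-sample standard error. Pooled, Welch and one-sample tests therefore share the same t.
- The pooled test refers it to 20 df (cut-off 2.086), Welch and one-sample to 10 df (cut-off 2.228). On 10 df, 2.086 has a two-sided tail of 6.4%.

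**A few ketamine waves.** Assume each ketamine patient shows a wave with probability q. The chance that the arm supplies at most one value is (1−q)¹¹ + 11q(1−q)¹⁰.

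| Assumed q | No values | At most one value |
|---|---|---|
| 5% | 57% | 90% |
| 10% | 31% | 70% |
| 20% | 9% | 32% |

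**Presence per patient.** With k/11 under methohexital and 0/11 under ketamine, Fisher's two-sided p = 2 × C(11,k)/C(22,k).

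- k = 4: 2 × 330/7,315 = .090.
- k = 5: 2 × 462/26,334 = .035.

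At k = 4 the uncorrected chi-square gives p = .027 with a smallest expected count of 2.0, so chi-square and exact test disagree at that boundary.

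**Power of a fixed-window measure.** Simulation, 11 per arm, two-sided 5%. Assumed: lognormal background power in every patient (log-SD 0.5), plus waves with median 3 to 10 times background (log-SD 1) in 50%, 60% or 70% of methohexital patients and in no ketamine patients. Each range runs from 3 times to 10 times background.

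| Test | 50% | 60% | 70% |
|---|---|---|---|
| t-test, raw power | 45–51% | 61–67% | 74–79% |
| Rank-sum | 47–53% | 64–71% | 80–85% |
| t-test, log power | 57–74% | 74–88% | 87–96% |

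**The case against.** The best reply is that the plan does not say power is measured only on detected waves. The opening phrase of that sentence leads into epoch-based ictal power for all patients, and the unspecified smaller epochs could be fixed windows. That stands as far as it goes: a fixed-window measure is not excluded. But none is defined, and suppression following an infra-slow wave can exist only where a wave was found. The absence of ketamine waves is likewise an expectation, not a rule, but the third outcome above covers the case where it fails.

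Three stronger readings are tempting, and the documents do not support them.

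- A reader might infer that Hypothesis 1.2 cannot be tested. It speaks of an association with infra-slow waves and does not mention power. The plan already has a chi-square on wave number, which could be run on presence per patient.
- A reader might infer from the 20 versus 10 df that the pooled test inflates false positives. That mismatch arises only when ketamine is all zero, which is the alternative. With equal zero-inflated arms (assumed log-SD 1), the pooled test rejected 3.2% of the time with waves in half the patients and 2.0% with waves in a quarter.
- A reader might infer that a rank-sum test is needed and would gain a great deal of power. With ketamine all zero, the exact rank-sum p-value equals Fisher's on presence, so its apparent advantage comes from a presence test. On a fixed-window measure its gain over the raw t-test is small, and a t-test on log power does better under the assumptions above.

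**Conclusion.** The defect is real and narrow. On the plan's own expectation, the between-arm t-test of infra-slow power has no ketamine values or a constant ketamine arm; otherwise it compares subsets formed after randomisation. This goes beyond missing detail, because a stated analysis cannot deliver what it is meant to deliver. It rests on reading the waves noted as the unit of measurement, which the text favours but does not state outright.

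No specific loss of power can be put on it, because wave rates and skewness are not in the documents. The fixed-window figures are illustrations over an assumed range. The t-tests of ictal power and post-ictal suppression in the same sentence are not touched. The pilot status of the trial does not remove the point, since Section 1 aims to identify a biomarker and infra-slow power is one of the candidates. The change should be made before the recordings are analysed.

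**What to change.** In Section 13:

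1. Define one post-ictal window and one infra-slow band in advance. Compute band power in them for every randomised patient with a recording, whether or not a wave is noted. State how a patient's recordings from T1 to T4 combine into one value.
2. Compare the arms on log power by t-test, or by a permutation or rank-sum test. Name the choice in advance, and name both arms in the sentence.
3. Label power among wave-positive patients as descriptive.
4. Compare presence of a wave per patient, yes or no, by an exact test in place of the chi-square.

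The cost is wording and some signal processing. Section 16 already provides about 30 minutes of 24-channel recording before and after ECT that includes the low-frequency range, so no visit or measurement is added. There are two small downsides. The effect is reported as a ratio of geometric means or a rank shift instead of a mean difference. Background power also dilutes the contrast, more so if waves are small relative to background, as the lower ends of the ranges for waves at 3 times background show.

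### Hypothesis 1.1 has two EEG parts joined by *and*, but the plan has no rule for when it is supported, and the stated .8 power at two-sided .05 fits neither a both-parts nor an either-part rule

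*Combined protocol and SAP*

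**What the plan says.** Section 1 (Aim 1) states "Hypothesis 1.1: Ketamine will be associated with increased ictal power and increased post-ictal suppression compared to methohexital". The general hypothesis just before it joins ictal and post-ictal changes with *or* when it describes the effect of the anesthetic.

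Section 5 bases the sample size on a published comparison of ictal power, with "Cohen's $d = 1.19$) with variances of .24 and .25 respectively". It concludes: "Assuming a power of .8 and a two-sided alpha (.05), we will need 11 patients in each group to adequately power our analysis". Recruiting 26 "allows for a conservative 15% attrition rate leaving a final sample size of 22".

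Section 13 opens by sending the reader to that calculation for Hypothesis 1.1, with no restriction to its ictal-power part. It then plans a chi-square test on the number of infra-slow waves and "t-tests to compare power of infra-slow waves and total ictal power of seizures and post-ictal suppression". That sentence ends by naming only the methohexital arm, so the comparison is not fully specified.

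The documents give no order of testing, alpha split, exploratory label or rule for declaring Hypothesis 1.1 supported. The outcomes called primary do not fill the gap: change in depression rating (Section 7; QIDS in Section 12), and HVLT-R percent retention for cognition (Section 12). None is an EEG comparison between arms.

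**The concern.** A two-part hypothesis with one test per part needs a stated rule, because three outcomes are possible: both tests significant, neither, or exactly one. In the third case the plan is silent, and the verdict could be settled after the data are seen.

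The choice also determines what the stated error rates mean. An either-part rule gives two chances to reject, so the false-positive rate exceeds .05. A both-parts rule keeps that rate at or below .05, but its power is below that of one test. Section 5's pair of figures, .8 and .05, therefore describes the ictal-power test and not Hypothesis 1.1 under either rule. Since Section 13 carries the calculation over to the whole hypothesis, a reader would take Hypothesis 1.1 to be powered at .8.

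**Working it through.** **Inputs from the documents.** d = 1.19, two-sided alpha .05, power .8, 11 per arm, 26 recruited, 15% attrition (Section 5). Two outcomes in Hypothesis 1.1 (Section 1), each compared by t-test (Section 13).

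**Assumptions.** The tests compare ketamine with methohexital, as Hypothesis 1.1 requires. The correlation between the two measures within an arm is 0 to 0.8. Post-ictal suppression has the same d = 1.19 as ictal power. The documents give neither the correlation nor the suppression effect.

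**Step 1: reproduce the plan's figure.**
- Normal approximation, n per arm = 2 × ((1.960 + 0.842) / 1.19)² = 11.09. The plan states 11; strict rounding up gives 12.
- Power at 11 per arm, normal approximation: Φ(1.19 × √(11/2) − 1.960) = Φ(2.791 − 1.960) = 79.7%.
- Power at 11 per arm for the t-test actually planned (noncentral t, 20 degrees of freedom, noncentrality 2.791, critical value 2.086): 75.6%.
- Attrition: 26 × 0.85 = 22.1, so 22 remain.

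The plan's .8 is thus reproduced for one test under the normal approximation. The t-test gives about 4 points less.

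**Step 2: either-part rule, no true effect.** For independent tests the false-positive rate is 1 − 0.95² = 9.75%. Correlated measures were simulated as two normal outcomes, 11 per arm, each tested by a two-sample t-test at two-sided .05.

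**Step 3: both-parts rule, d = 1.19 on each measure.** For independent tests, power is 0.756² = 57%. The same simulation covers the correlated cases. The share of trials with exactly one significant test is the share with at least one minus the share with both.

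| Correlation | Either rule: false-positive rate | At least one significant, both effects real | Both significant | Exactly one significant |
|---|---|---|---|---|
| 0 | 9.8% | 94% | 57% | 37% |
| 0.5 | 9.2% | 89% | 63% | 26% |
| 0.8 | 7.9% | 84% | 67% | 17% |

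**Step 4: what does not depend on the suppression assumption.** The chance that both tests are significant cannot exceed the chance that the ictal-power test is. So both-parts power is at most 75.6% by t-test (79.7% by normal approximation), however large the suppression effect. A suppression effect below 1.19 lowers it beneath the tabulated values.

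**Step 5: how much is due to the t distribution.** Starting from the nominal 80%, both-parts power is 0.8² = 64% at correlation 0 and 69% at 0.5. The shortfall remains after the t-versus-normal difference is removed.

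**The case against.** Four points can fairly be made for the plan.

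- **The wording already implies a rule.** Hypothesis 1.1 says *and*, which reads naturally as both parts, and Section 5 sizes on ictal power, which suggests a lead measure. It would be too strong to say that the plan gives no indication of a deciding test. But the two hints point to different rules: *and* makes suppression necessary, while the sizing makes ictal power decisive. Neither is written down.
- **This is a pilot.** Strict error control across all outcomes is not obligatory in a 26-patient study looking for candidate biomarkers. That stands, and the point does not ask for it. Even so, the plan states a directional hypothesis and claims adequate power for it, so it should say what that claim covers.
- **The power figures are conditional.** They depend on an unstated correlation and an unstated suppression effect, and about 4 points of the gap from 80% come from the t distribution. A reader might infer that the power of Hypothesis 1.1 is about 62% instead of 80%. The documents support only a range under stated assumptions, plus the ceiling in Step 4.
- **Hypotheses 1.1 and 1.2 are separate.** A reader might count all four EEG tests and infer a false-positive risk of about 16% for some effect of the anesthetic. The documents do not support using that figure. It pools two hypotheses about different phenomena into a single success claim that the plan does not make. It also assumes a correlation of 0.5 and treats the wave-count chi-square as a .05-level t-test. At 11 per arm, an uncorrected chi-square on presence of waves has an actual size anywhere from 0.2% to 5.3% for event rates of .05 to .5, and counting several waves per patient could push it the other way.

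**Conclusion.** The point holds for Hypothesis 1.1. The plan applies a one-test power statement to a two-part hypothesis and gives no rule for a split result. At 11 per arm, an either-part rule has a false-positive rate of about 8 to 10% (correlation 0.8 down to 0). A both-parts rule has about 57 to 67% power (correlation 0 up to 0.8, d = 1.19 assumed for suppression) and at most about 76% by t-test. If both effects are real at that size, about 17 to 37% of trials would leave the hypothesis without a defined verdict.

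All of this rests on reading the Section 13 tests as comparisons between arms, which its sentence leaves unclear. The conclusion that neither rule has the stated properties holds at every correlation examined. It does not extend to a family-wise failure over all four EEG tests, and it does not imply that Hypothesis 1.2 must be relabelled.

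**What to change.** **Section 13.** State that Hypothesis 1.1 is decided by total ictal power, ketamine versus methohexital, by t-test at two-sided .05, and that post-ictal suppression is compared between the same arms at two-sided .05 only if ictal power is significant. Correct the end of the t-test sentence so that the comparator is explicit for each measure. With this order, the chance of any false claim within Hypothesis 1.1 stays at or below .05: if ictal power has no true effect, a false claim requires that test to reject; if it has one, only the suppression test can err.

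**Section 5.** State that the power figure applies to the ictal-power test only, about 76% by t-test at 11 per arm (80% by normal approximation), and not to Hypothesis 1.1 jointly or to Hypothesis 1.2.

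**Cost.** Text changes only. The ictal-power test keeps its full alpha and its power, and no patients are added. The downside is that suppression cannot be claimed if ictal power is not significant. A sponsor who wants Hypothesis 1.1 to require both parts can write that rule, but 80% joint power would then need about 15 per arm (correlation 0.5) to 16 per arm (correlation 0) at d = 1.19 for each measure. Splitting alpha equally over the two tests would leave about 65% power per test at 11 per arm.

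Whether Hypothesis 1.2 is labelled exploratory is for the sponsor to decide.
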